## 6.2.11 Concentration-Time Data

Blood Samples for PK analysis in plasma will be collected at:

Part 1 (SAD):

- Predose, and 0.5, 1, 2, 3, 4, 5, 6, 8, 10, 12, 16, 20, 24, 28, 32, 36, 40, 44, 48, 54, 60, 66, 72, 80, 88, 96, 120, 144, and 168 hours after dosing, then on Days 10, 14, 17, 21 and 28.

Additional samples will be drawn on Days 42, 56, and 70 for Cohorts 4, 5, and 6.

- For Cohort 7, PK samples will be collected at predose (0), and 0.5, 1, 2, 3, 4, 5, 6, 8, 10, 12, 16, 20, 24, 28, 32, 36, 40, 44, 48, 54, 60, 66, 72, 80, 88, 96, 120, 144, and 168 hours (Day 14) after dosing.

Part 1 (FE):

- Predose, and 0.5, 1, 2, 3, 4, 5, 6, 8, 10, 12, 16, 20, 24, 28, 32, 36, 40, 44, 48, 54, 60, 66, 72, 80, 88, 96, 120, 144, and 168 hours after dosing, then on Days 10, 14, 17, 21 and 28.

Part 2 (MAD):

- Day 1: Predose, and 0.5, 1, 2, 3, 4, 5, 6, 8, 10, 12, 16, 20, 24 (pre-dose sample for Day 2).

QMD Ref: Worldwide-TMP-ST-006-4.0 Effective: 12Aug2019	Governing QMD: Worldwide-SOP-ST-001
Confidentiality Statement	

This document is the property of Worldwide Clinical Trials Inc. and may not be duplicated, copied, altered or removed from company without prior approval from Worldwide Quality Assurance or in compliance with Worldwide Standard Operating Procedures.

Worldwide Clinical Trials Controlled Quality Management Document		
 WORLDWIDE CLINICAL TRIALS	Sponsor:	Global Alliance for TB Drug Development
	Protocol Number:	TBAJ-876-CL001
STATISTICAL ANALYSIS PLAN – PHASE 1		

- Day 14: 0.5, 1, 2, 3, 4, 5, 8, 12, 16, 20, 24, 28, 32, 36, 40, 44, 48, 54, 60, 66, 72, 80, 88, 96, 120, 144, and 168 hours after dosing and on Days 42, 63, 84, 105, and 126.
- Additional or fewer samples may be collected at times to be determined based on the results from previous cohorts. Predose trough concentrations will be collected daily from Days 2 through 13.

Part 3 (RBA and FE):

- Pre-dose, and 0.5, 1, 2, 3, 4, 5, 6, 8, 10, 12, 16, 20, 24, 28, 32, 36, 40, 44, 48, 54, 60, 66, 72, 80, 88, 96, 120, 144, and 168 hours after dosing, then on Days 10 (240 h) and 14 (336 h).

Concentration-time data will be tabulated by part, nominal time, analyte, cohort (group for Part 3), and study day (for Part 2) using descriptive statistics. For presentation of the individual data and summary statistics, concentrations below the limit of quantitation (BLQ) will be set to zero.

Mean and individual subject concentration-time data will be presented graphically on linear and semi-logarithmic scales.

For Part 1 (SAD), mean concentration-time data will be presented for all cohorts and for Part 1 (Food Effect), mean concentration-time data will be presented for fed vs. fasted cohorts.

For Part 2 (MAD), mean concentration-time data will be presented by day (all cohorts on Day 1 Day 14 separately), and by cohort (all days for each cohort). Mean concentration-time data will also be plotted for trough concentrations.

For Part 3 (RBA, FE), mean concentration-time data will be presented for all three groups; mean concentration-time plots will be presented for Groups 1 vs. 2 (100 mg tablets under fed and fasted conditions) and for Groups 1 vs. 3 (100 mg doses in different tablet strengths).

Mean data will be plotted using nominal sample times, and individual data will be plotted using actual times. For all subject plots (spaghetti plots, all subjects per cohort in one plot), subjects will be identified by subject number in the legend.

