Subjects will be confined in the clinic prior to dosing (Day -1) until 7 days after dosing (Day 8). Subjects will return to the clinic to have subsequent follow up safety and PK measurements on Days 10 and 14. A follow-up phone call to collect any AEs will be conducted on Day 21. Refer to the schedule of assessments in Table 17.

Blood samples will be obtained before each dose of study drug, and at serial time points postdose on Days 1-8 and Days 10 and 14. Plasma PK samples will be analyzed for TBAJ-876, M2 and M3 using validated analytical methods.

In addition, blood and urine will be collected for clinical laboratory evaluations.

Female subjects will have blood collected for serum pregnancy testing. Females claiming postmenopausal status will have blood collected to measure follicle stimulating hormone (FSH) levels.

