For Cohort 7, a total of 124 mL (31 x 4 mL samples) will be collected from each subject for PK analysis. Approximately 78.5 mL of blood will be collected for the clinical laboratory evaluations and coagulation testing. The total volume of blood collected from each subject in Part 1 Cohort 7 will not exceed approximately 203 mL.

6.7.2 Part 2

A total of 212 mL (53 x 4 mL samples) will be collected from each subject for PK analysis. Approximately 110.6 mL of blood will be collected for the clinical laboratory evaluations and coagulation testing. The total volume of blood collected from each subject in Part 2 is planned not to exceed approximately 322.6 mL, although more may be collected if a decision is made to prolong PK monitoring.

Table 9 Total Volume of Blood to be Collected for Testing: Part 2

Reason for Collection	Number of Samples	Volume per Sample (mL)	Total Volume (mL)
Clinical labs at screening	1	12.5	12.5
Clinical labs during study (check-in, Days 7, 14, 21, 42, 63, 84, 105, and 126 (end-of-study)	9	8.5	76.5
Coagulation	8	2.7	21.6
Pharmacokinetic analysis (predose trough)	13	4.0	52.0
Pharmacokinetic analysis (postdose)	40	4.0	160.0
		Total	322.6

Additional PK samples may be collected at times to be determined based on the results from previous cohorts.

The Principal Investigator, in conjunction with the Sponsor, may collect additional blood if necessary, for repeat laboratory or safety evaluations including AE follow-up.

6.7.3 Part 3

A total of 128 mL (32 x 4ml samples) will be collected for PK Analysis. Approximately 91 mL of blood will be collected for the clinical laboratory evaluations and coagulation testing.

Table 10 Total Volume of Blood to be Collected for Testing: Part 3

Reason for Collection	Number of Samples	Volume per Sample (mL)	Total Volume (mL)
Clinical labs at screening	1	12.5	12.5
Clinical labs during study (check-in, 6 and 48 hours and Days 5, 7, 10, and 14 (end-of-study).	7	8.5	59.5
Coagulation	7	2.7	18.9
Pharmacokinetic analysis	32	4.0	128.0
		Total	218.9

The Principal Investigator, in conjunction with the Sponsor, may collect additional blood if necessary, for repeat laboratory or safety evaluations including AE follow-up.

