- Urinalysis (pH, specific gravity, protein, glucose, micro-albumin, ketones, bilirubin, creatinine, nitrite, sodium, urobilinogen, myoglobin, blood, leukocytes). If protein, occult blood, nitrite, or leukocyte esterase values are out of range, a microscopic examination will be performed. Myoglobin will be collected but results will not be required for dose qualification.
- f. Female subjects will have a urine pregnancy test at the end-of-study on Day 14 or early withdrawal.
- g. Subjects will be monitored from the time of signing the informed consent and throughout the study via safety assessments, observation and subject reporting. A specific inquiry regarding AEs will be conducted prior to dosing and at time points specified postdose and upon return to clinic for subsequent visits.
- h. TBAJ-876 Tablet will be administered orally with 240 mL of water.
- i. Subjects will be followed up for safety and PK during follow-up at the following timepoints: pre-dose, 0.5, 1, 2, 3, 4, 5, 6, 8, 10, 12, 16, 20, 24, 28, 32, 36, 40, 44, 48, 54, 60, 66, 72, 80, 88, 96, 120, 144, and 168 hours after dosing, then on Days 10 and 14.
- j. Continuous 12-lead Holter recording (cardiac telemetry) will begin 1 hour before and end 24 hours after dosing.
- k. ECGs on Day 1 will be extracted from a continuous 12 lead Holter recording at discrete timepoints as noted in above flow chart and will be extracted at the same time as vital sign measurements. If a subject experiences a post-dosing QTcF >500 msec or a change-from-baseline QTcF >60 msec, after repeat testing, additional ECGs should be recorded until normalization or return to baseline. NOTE: when ECG extractions coincide with safety ECGs, vital sign assessments, and/or blood draws, then procedures should be carried out in said order.

Global Alliance for TB Drug Development

CONFIDENTIAL

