## 6.2.5 Study Day / Duration

Study day will be calculated as the number of days from first dose of study drug.

- date of event – date of first dose of study drug + 1, for events on or after first dose.
- date of event – date of first dose of study drug, for events before first dose.

Duration is calculated in hours as (event end date-time – event start date-time).

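### The SAP's hour labels for the Part 3 Day 10 and Day 14 samples are each 24 h late under its own study-day rule, and the Cohort 7 list omits a correct Day 14 time

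*SAP*

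**What the plan says.** SAP 6.2.5 counts study day as the event date minus the "date of first dose of study drug + 1, for events on or after first dose". The dosing day is therefore Day 1.

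SAP 6.2.11 follows this rule for the Part 2 profile, where the 24 h sample is described as "24 (pre-dose sample for Day 2". Protocol section 3 follows it for Part 3: "Subjects will be confined in the clinic prior to dosing (Day -1) until 7 days after dosing (Day 8".

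The late samples in SAP 6.2.11 do not follow it:

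- Part 3: sampling to 168 h, "then on Days 10 (240 h) and 14 (336 h". The protocol's footnote to Table 17 gives the same visits by day only: "and 168 hours after dosing, then on Days 10 and 14".
- Part 1, Cohort 7 (800 mg): the list ends "and 168 hours (Day 14) after dosing".

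Protocol 6.7.1 states: "For Cohort 7, a total of 124 mL (31 x 4 mL samples) will be collected from each subject for PK analysis". SAP 3.1 says Cohort 7 had an additional sample on Day 14, and protocol section 3 schedules a Day 14 visit for PK.

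On how times are used, SAP 6.2.11 and 6.3 tabulate concentrations by nominal time. Mean profiles are plotted on nominal times and individual profiles on actual times. SAP 6.2.12, which defines the NCA, does not say which times it uses.

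**The concern.** The hour labels conflict with the study-day definition in the same document. Whoever programs the tables and mean plots from SAP 6.2.11 will place the last two Part 3 points a full day late. The allowed sampling window after Day 7 is ±10 minutes (protocol Table 11), so a 24 h error is 144 times that window. For Cohort 7 the programmer has one label that attaches two different study days to one sample, and no time for the sample that was actually planned on Day 14.

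The late points also carry the terminal slope, and with it half-life, AUCinf and CL/F. If the nominal labels reached the NCA, those parameters would be affected too. The SAP neither states nor excludes this.

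**Working it through.** **Step 1: reproduce the SAP's figures.** 240 = 10 × 24 and 336 = 14 × 24, so the labels come from day × 24, which treats the dosing day as Day 0. That rule fails the documents' own anchors:

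| Study day | (day − 1) × 24 | day × 24 | What the documents say |
|---|---|---|---|
| 2 | 24 h | 48 h | 24 h (SAP 6.2.11) |
| 8 | 168 h | 192 h | 7 days = 168 h (protocol section 3) |
| 10 | 216 h | 240 h | 240 h (SAP 6.2.11, Part 3) |
| 14 | 312 h | 336 h | 336 h (SAP 6.2.11, Part 3) |

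Under the SAP 6.2.5 rule, 240 h is Day 11 and 336 h is Day 15.

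**Step 2: count the samples.** Predose to 168 h gives 30 times. Part 3 adds Days 10 and 14, so 30 + 2 = 32, which matches the protocol's 32. Cohort 7 adds Day 14, so 30 + 1 = 31, which matches the protocol's 31 (31 × 4 mL = 124 mL). The SAP's Cohort 7 list stops at 30. It therefore has a wrong day label and is one time short.

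**Step 3: half-life, only if NCA used the nominal labels.** Take a log-linear decline through the last three Part 3 points.

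- True times 168, 216, 312 (mean 232): deviations −64, −16, 80.
- Labels 168, 240, 336 (mean 248): deviations −80, −8, 88.
- Sum of squares of the labels: 6400 + 64 + 7744 = 14208. Cross-product: 5120 + 128 + 7040 = 12288.
- Fitted slope / true slope = 12288/14208 = 0.865, so fitted half-life / true half-life = 1.156.

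That is +15.6% at any true half-life. Using the last 4, 5 or 6 points gives +16.5%, +15.7% and +14.3%. A 168 h half-life would be reported as about 190-196 h. The fit would pass the SAP's check: adjusted R² is 0.977 or higher, against the 0.80 limit in SAP 6.2.12.4.

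**Step 4: AUC, same condition, at the 7-day planning half-life (protocol section 3).** Assume mono-exponential decline from 1. The concentrations at 168, 216 and 312 h are 0.500, 0.410 and 0.276.

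- Area 0-168 h: 0.5 × 168/ln 2 = 121.2.
- Trapezoids after 168 h, true times: 48 × 0.455 + 96 × 0.343 = 54.8.
- The labels widen the first of these intervals from 48 to 72 h, adding 24 × 0.455 = 10.9.
- AUClast: 10.9/(121.2 + 54.8) = +6.2%.
- Tail: 0.276 × 168/ln 2 = 66.9 true; 66.9 × 1.156 = 77.4 on labels.
- AUCinf: (176.0 + 10.9 + 77.4)/(176.0 + 66.9) = 264.3/242.9 = +8.8%.

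Running the full sampling grid gives AUClast +6.3% for this profile. For an assumed bi-exponential profile (70% fast phase, 12 h half-life) it gives +5.2%. AUCinf is about +7% to +9%, depending on the profile and the number of regression points. Over assumed half-lives of 77-336 h, AUClast is +3% to +7% and AUCinf about +4% to +12%.

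**Step 5: Part 3 ratios.** All three groups carry the same labels. In an illustration with a common 168 h half-life, the AUClast ratio is 1.475 on true times and 1.476 on labels.

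**The case against.** The strongest reply is that the harm is confined to presentation. SAP 6.2.11 uses nominal times for tables and mean plots and actual times for individual plots. Lambda-z is fitted to a range chosen by inspecting a semi-logarithmic plot. Actual sampling times are recorded (protocol Appendix 1) and PK sampling data are listed (SAP Listing 16.2.5.1). On that reading NCA runs on actual times and the bias in steps 3 and 4 is zero. This stands as far as it goes: the documents point towards actual times but do not say so.

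Three stronger readings are tempting and are not supported:

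- *Half-life and AUC will be biased.* The SAP never says NCA uses nominal times. The step 3 and step 4 figures are conditional.
- *The SAP drops the last 800 mg sample.* SAP 3.1 and the protocol both have a Day 14 sample for Cohort 7. AUClast runs to the last quantifiable concentration, not to the last listed time, and nothing in the SAP excludes a collected Day 14 value. A wording slip with one time missing is the more natural reading.
- *Ending Cohort 7 at 168 h decides whether AUCinf is reported.* At a 7-day half-life with mono-exponential decline, the extrapolated share is 2^(−168/168) = 50% ending at 168 h and 2^(−312/168) = 28% ending at 312 h. Both exceed the 20% limit in SAP 6.2.12.4, so the reporting outcome does not change.

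It is also fair that Cmax and AUC0-24h are untouched, that the lists for Cohorts 1-6 and the Part 1 food-effect cohort give late visits by day without hours and so contain no such error, and that the safety objective is unaffected.

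**Conclusion.** The labels are wrong as written and should be corrected. Two effects are certain if SAP 6.2.11 is followed: the Part 3 nominal-time tables and mean profiles are 24 h late at Days 10 and 14, and the Cohort 7 Day 14 sample has no correct nominal time.

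The effect on parameters depends on NCA using nominal times. If it did, absolute Part 3 half-life, AUC and CL/F, and comparisons of them with Part 1, would be exposed to the errors shown above. Those sizes rest on noise-free profiles and, for AUC, on the 7-day planning half-life. The Part 3 food-effect and tablet-strength ratios are essentially unaffected under either choice of times.

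**What to change.** In SAP 6.2.11:

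- Part 3: give Day 10 as 216 h and Day 14 as 312 h.
- Cohort 7: end the list with 144 and 168 hours (Day 8), then Day 14 (312 h), which restores 31 samples.

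In SAP 6.2.12, state that NCA uses actual elapsed times from dosing.

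These are the values the SAP's own study-day rule implies. If sampling at 240 h and 336 h was truly intended, the visit days in the protocol and SAP must be reconciled with those hours instead. On the first route the cost is SAP wording only, with no change to visits, samples or sample size.

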## 6.2.12 PK Analysis

Concentration-time data for TBAJ-876, M2, and M3 will be analyzed using noncompartmental methods in Phoenix™ WinNonlin® (Version 8.1 or higher, Certara, L.P.) in conjunction with the internet-accessible implementation of Pharsight® Knowledgebase Server™ (PKSO; Version 4.0.4, Certara, L.P.).

QMD Ref: Worldwide-TMP-ST-006-4.0 Effective: 12Aug2019	Governing QMD: Worldwide-SOP-ST-001
Confidentiality Statement	

This document is the property of Worldwide Clinical Trials Inc. and may not be duplicated, copied, altered or removed from company without prior approval from Worldwide Quality Assurance or in compliance with Worldwide Standard Operating Procedures.

Worldwide Clinical Trials Controlled Quality Management Document					
 WORLDWIDE CLINICAL TRIALS	Sponsor:	Global Alliance for TB Drug Development			
Protocol Number: TBAJ-876-CL001					
STATISTICAL ANALYSIS PLAN – PHASE 1					

During the pharmacokinetic analysis, concentrations below the limit of quantitation (BLQ) up to the time of the first quantifiable concentration will be treated as zero. Embedded (values between 2 quantifiable concentrations) and terminal BLQ concentrations will be treated as “missing”.

### 6.2.12.1 Part 1 PK Parameters

The following PK parameters will be calculated for TBAJ-876, M2, and M3 for Part 1:

Parameter	Definition
C max	Maximum plasma concentration, determined directly from individual concentration-time data
T max	Time of the maximum plasma concentrations
C last	Last quantifiable plasma concentration determined directly from individual concentration-time data
T last	Time of last quantifiable plasma concentration
AUC last	Area under the plasma concentration-time curve from time-zero to the time of the last quantifiable concentration (C last ), as calculated by the linear trapezoidal method
AUC 0-24h	Area under the plasma concentration-time curve from time-zero to 24 h postdose, as calculated by the linear trapezoidal method
AUC 0-72h	Area under the plasma concentration-time curve from time-zero to 72 hours postdose, as calculated by the linear trapezoidal method
AUC inf	Area under the plasma concentration-time curve from the time of dosing extrapolated to infinity, calculated as:  AUC inf = AUC last + C last /λ z , where λ z is the apparent terminal elimination rate constant calculated by linear regression of the terminal linear portion of the log concentration versus time curve
AUC Extrap	The percentage of AUC inf based on extrapolation, calculated as:

QMD Ref: Worldwide-TMP-ST-006-4.0 Effective: 12Aug2019	Governing QMD: Worldwide-SOP-ST-001
Confidentiality Statement	

This document is the property of Worldwide Clinical Trials Inc. and may not be duplicated, copied, altered or removed from company without prior approval from Worldwide Quality Assurance or in compliance with Worldwide Standard Operating Procedures.

Worldwide Clinical Trials Controlled Quality Management Document					
 WORLDWIDE CLINICAL TRIALS	Sponsor:	Global Alliance for TB Drug Development			
Protocol Number: TBAJ-876-CL001					
STATISTICAL ANALYSIS PLAN – PHASE 1					

Parameter	Definition
	$(1 - \text{AUC}_{\text{last}}/\text{AUC}_{\text{inf}}) * 100$ (see additional criteria in Section 6.2.12.3)
$\lambda_z$ (K el , Lambda z)	The apparent elimination rate constant $\lambda_z$ will be calculated as the negative of the slope of the linear regression through the terminal log-linear segment of the plasma concentration-time curve; the range of data to be used will be determined by visual inspection of a semi-logarithmic plot of concentration vs. time (see additional criteria in Section 6.2.12.3)
t 1/2	The observed terminal elimination half-life, calculated as: $t_{1/2} = \ln(2)/\lambda_z$
CL/F	The apparent total plasma clearance after an oral dose, calculated as: CL/F=Dose/AUC inf , where F is the bioavailability (calculated for parent only)
Vz/F	The apparent volume of distribution after an oral dose, calculated as: Vz/F=Dose/(AUC inf x $\lambda_z$ ), where F is the bioavailability (calculated for parent only)

### 6.2.12.2 Part 2 PK Parameters

#### 6.2.12.2.1 Study Day 1 PK Parameters (Part 2)

The following PK parameters will be calculated for TBAJ-876, M2, and M3 for Part 2 (Day 1):

Parameter	Definition
C max	Maximum plasma concentration, determined directly from individual concentration-time data
T max	Time of the maximum plasma concentrations

QMD Ref: Worldwide-TMP-ST-006-4.0 Effective: 12Aug2019	Governing QMD: Worldwide-SOP-ST-001
Confidentiality Statement	

This document is the property of Worldwide Clinical Trials Inc. and may not be duplicated, copied, altered or removed from company without prior approval from Worldwide Quality Assurance or in compliance with Worldwide Standard Operating Procedures.

Worldwide Clinical Trials Controlled Quality Management Document			
 WORLDWIDE CLINICAL TRIALS	Sponsor:	Global Alliance for TB Drug Development	
	Protocol Number:	TBAJ-876-CL001	
STATISTICAL ANALYSIS PLAN – PHASE 1			

Parameter	Definition
$C_{last}$	Last quantifiable plasma concentration determined directly from individual concentration-time data
$T_{last}$	Time of last quantifiable plasma concentration
$AUC_{0-24h}$ ( $AUC_{tau}$ )	Area under the plasma concentration-time curve over the 24 hour dosing interval, calculated using the linear trapezoidal rule
$C_{avg}$	Average plasma concentration over 24 hours
$C_{24}$	Plasma concentration at 24 hours postdose
$\lambda_z$ ( $K_{el}$ , Lambda z)	
The apparent elimination rate constant <math>\lambda_z</math> will be calculated as the negative of the slope of the linear regression through the terminal log-linear segment of the plasma concentration-time curve; the range of data to be used will be determined by visual inspection of a semi-logarithmic plot of concentration vs. time
 
(see additional criteria in Section 6.2.12.3)
 
(may be calculated as reasonable)

$t_{1/2}$	
The observed terminal elimination half-life, calculated as:
 $t_{1/2} = \ln(2)/\lambda_z$ 
(may be calculated as reasonable)

$CL/F$	
The apparent total plasma clearance after an oral dose, calculated as:
 $CL/F = Dose/AUC_{inf}$ , where F is the bioavailability 
(calculated for parent only, may be calculated as reasonable)

$Vz/F$	
The apparent volume of distribution after an oral dose, calculated as:
 $Vz/F = Dose/(AUC_{inf} \times \lambda_z)$ , where F is the bioavailability 
(calculated for parent only, may be calculated as reasonable)

